3.3. Screening Procedures

Physiological measures collected and recorded on paper, and entered into REDCap by the interviewer at the end of the visit:

- 1. Breath alcohol concentration (BrAC)
- 2. Expired breath carbon monoxide (CO).
- 3. Urinary cotinine strips, if needed
- 4. A urine toxicological screen
- 5. Weight and height
- 6. Pregnancy Tests (HCG detection)
- 7. Blood pressure and heart rate

Screening questionnaires administered on paper and entered into the study databases at the end of the visit:

- 1. Identifying Information Form
- 2. Brief Medical History Questionnaire
- 3. Prime MD

Screening assessments administered via interview and entered into REDCap by the interviewer:

- 1. Concomitant Medications Form
- 2. The Mini International Neuropsychiatric Interview (MINI) suicide subscale
- 3. Tobacco Use History Questionnaire
- 4. Smoking Cessation Therapy Use Questionnaire
- 5. Drug Use Questionnaire (12 month and 1 month version)

Assessments administered on paper and kept as a source document only:

- 1. Brief Medical History Follow-Up Questionnaire, if needed
- 2. BDI, if needed
- 3. GAD 2 week monitoring, if needed

Screening assessments administered directly via Redcap:

- 1. Demographic Questionnaire
- 2. Center for Epidemiological Studies-Depression Scale
- 3. Alcohol Use Questionnaire (12 month and 1 month version)
- 4. Smoking Stages of Change

If the Redcap website is not functioning, the assessments will be printed out and administered on paper. The source documents will be kept in the participant's binder. The interviewer will enter the data into Redcap when it resumes functioning properly. This information should be recorded in the 'End of Visit Evaluation Form' and entered in to REDCap.

The following task will be completed after initial eligibility determination by the research assistant (prior to review by medical staff):

1. Puff topography entails having participants smoke through a device that more precisely measures puffing behavior (e.g., puff volume). At screening, participants will smoke a usual brand cigarette through the topography device.

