6.4. Visit 01, 02, 03, 04, 06, 08, 10, and 12 Procedures

Physiological measures collected and recorded on paper, and entered into REDCap at the end of the visit:

- 1. BrAC
- 2. Weight
- 3. CO
- 4. Blood Pressure
- 5. Heart Rate
- 6. Urine toxicology assessment (Visit 12 only)
- 7. Pregnancy test (if applicable, Visits 4, 8, 12 only)

Biological specimens collected, stored, and entered into CENIC Biosamples Collection Platform:

1. First void urine sample for smoking biomarker assessment (Visits 4, 8, 12):

Participants will be asked to bring a urine sample (first void of the day) for biomarker assessment. Samples will be stored at temperatures approximately at -20°C (UPenn) or -80°C (Wake Forest). Urine samples will be sent regularly to be analyzed and stored at the University of Minnesota. We will assess mercapturic acids, and total nicotine equivalents (TNEs). If a participant forgets to bring his/her urine sample, then the spot urine sample will be used.

2. Spot urine sample for assessing baseline anatabine:

Participants will be asked to provide a urine sample in the lab for biomarker assessment. Samples will be stored at temperatures approximately at --20°C (UPenn) or -80°C (Wake Forest). Urine samples will be sent regularly to be analyzed and stored at the University of Minnesota.

Assessments administered via interview and entered into REDCap by the interviewer:

- 1. Concomitant Medications
- 2. Adverse Event Form, if applicable
- 3. Health Changes Questionnaire
- 4. IVR Review of Daily Call and follow-up on missing and unusual reports and Timeline Follow-back Questionnaire; if needed
- 5. Intention to Quit Smoking and Vaping
- 6. Drug Use Questionnaire, 1 month version (Visits 4, 8, 12)

Assessments administered on paper and kept as a source document only:

- 1. BDI, if applicable
- 2. GAD 2 week monitoring, if needed

Assessments administered directly via REDCap:

- 1. Respiratory Health Questionnaire
- 2. MNWS
- 3. Urge to Use Questionnaire-Experimental
- 4. Perceived Health Risks Questionnaire: Study Products (Visits 2, 4, 8, 12)
- 5. CESD (Visits 4, 8, 12)
- 6. Alcohol Use Questionnaire, 1 month version (Visits 4, 8, 12)
- 7. Context of Product Use-Experimental Version (Visits 4, 8, 12)
- 8. Smoking Stages of Change (Visits 4, 8, 12)
- 9. Cigarette and Vaping Dependence Questionnaires (Visits 4, 8, 12)
- 10. Purchase task-Study Cigarette + Vape Version (Visit 12)
- 11. Smoking and Vaping Expectancies Questionnaires (Visit 12)

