Participants who make any response other than "not at all" on the suicidal ideation question of the Prime MD (Question 1i), indicate suicidal ideation, have attempted suicide in the past month, or have had a suicide attempted in the past 5 years on the MlNI suicide subscale will not be eligible to participate in the study. If the participant has attempted suicide between 6-10 years ago, then the LMM must approve eligibility. To determine if a participant is in immediate danger, staff will ask the participant two questions to determine level of risk: "Are you feeling suicidal?" and "Do you have a plan to kill yourself today?" If the participant has a plan to kill himself/herself, staff will put the participant in contact with the suicide prevention hotline (Durham Center Crisis Line at [name]; Philadelphia Suicide Prevention [contact] or UPenn's HELP line: [name]). If the participant refuses to talk to the hotline and leaves, the study staff will call 911. They will also contact the Study Coordinator and Site PI to inform them of the situation as soon as possible. If the participant does not have a plan to kill himself/herself, the study staff will recommend he/she speaks with the suicide hotline. The visit will continue as normal, but the participant will not be eligible for the study. The participant will be paid \$30 and provided with local mental health resources. The on-site clinician will be available by phone for consultation within 24-hours.

Additionally, any participant whose score on the Prime MD indicates Major Depressive Disorder will be administered the Beck Depression Inventory (BDI) and the GAD 2 week monitoring on paper. The BDI will be submitted, along with the Prime MD, Brief Medical History Questionnaire, Brief Medical History Follow-up Questionnaire, and the MINI suicide subscale to the licensed medical monitor for eligibility review. If he/she determines a participant with Major Depressive Disorder is eligible for study participation, the participant will complete the BDI each visit to monitor changes in his/her mood.

21. Adverse Events (AE)

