- 2. Respiratory Health Questionnaire: In the past week, have you experienced any health problems, such as cold, flu, or other respiratory illness that would affect these respiratory symptoms?

No new AE report will be required if one or more conditions below are met and the description does not otherwise meet the definition of an AE.

- a. Existing AE already open for reported symptom
- b. Pre-existing condition without increase in severity or frequency of symptoms (brief medical history will be updated if not previously reported; e.g., seasonal allergies).
- 3. CESD: If the participant **scores 16 or higher and is not already being monitored for depression**, a 'Adverse Event Form' should be completed and the LMM will provide information regarding follow-up. If there is already an open event, information will be added to the existing 'Adverse Event Form.'

Physiological data that will be reviewed:

- 1. CO level: The 'Adverse Event Form' should be completed if the average CO within a visit is:
 - o CO is greater than 50 ppm if CO at Baseline is < 20 ppm.
 - CO is greater than 60 ppm if CO at Baseline is 20 34 ppm.
 - o CO is greater than 70 ppm if CO at Baseline is 35 49 ppm.
 - CO is greater than 80 ppm if CO at Baseline is 50 64 ppm.
 - CO is greater than 90 ppm if CO at Baseline is 65 80 ppm.

2. Blood Pressure:

- The 'Adverse Event Form' and 'Blood Pressure and Heart Rate Symptom Checklist' should be completed if an automatic and subsequent manual blood pressure measurement during the same visit is at or above 160 SBP or 100 DBP.
- The 'Adverse Event Form' and 'Blood Pressure and Heart Rate Symptom Checklist' should be completed if an automatic and subsequent manual blood pressure measurement during the same visit is below 90 SBP or 50 DBP.

3. Heart Rate:

- The 'Adverse Event Form' and 'Blood Pressure and Heart Rate Symptom Checklist' should be completed if an automatic and subsequent manual heart rate measurement during the same visit is at or above 105 bpm.
- The 'Adverse Event Form' and 'Blood Pressure and Heart Rate Symptom Checklist' should be completed if an automatic and subsequent manual heart rate measurement during the same visit is below 45 bpm.

22. Management of SAEs and Other Study Risks

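### For participants not already monitored for depression, the CES-D adverse event trigger ignores the screening score, so unchanged or improved symptoms can be recorded as adverse events

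*Combined protocol and SAP*

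**What the plan says.** CES-D is administered at screening; section 3.3 lists the "Center for Epidemiological Studies-Depression Scale". It is repeated at Visits 4, 8 and 12 (sections 6.4 and 32). None of the exclusion criteria in section 3.6 refers to a CES-D score. The psychiatric exclusions cover unstable conditions, schizophrenia and schizoaffective disorder, and suicidality.

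Section 21.1 item 3 calls for an Adverse Event Form if the participant "scores 16 or higher and is not already being monitored for depression", with the medical monitor advising on follow-up. If an event is already open, the new information goes on the existing form.

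The entry route into depression monitoring that the plan describes is in section 20 and uses another instrument: "any participant whose score on the Prime MD indicates Major Depressive Disorder will be administered the Beck Depression Inventory (BDI"). If such a person is accepted, "the participant will complete the BDI each visit to monitor changes in his/her mood".

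Items 1b and 2b of section 21.1, for the Health Changes and Respiratory Health questionnaires, waive a new report for a "Pre-existing condition without increase in severity or frequency of symptoms". Item 3 has no such clause.

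Section 28.4 lists both change in CES-D and adverse events as safety outcomes.

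**The concern.** Item 3 records a state, whereas an adverse event table is normally read as recording change. Someone who screens at 24 and scores 18 at Visit 4 has improved, but if unmonitored still gets an Adverse Event Form. The Adverse Event Form is first scheduled at the Baseline visit, and CES-D is not repeated until Visit 4. A high screening score therefore opens nothing at entry and surfaces only after randomisation, where it looks like an on-treatment event.

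Mood change is a named risk of altering nicotine intake (section 17, item 11), so mood events will be examined. If the count mixes people who were already symptomatic with people who newly crossed the threshold, the total overstates how often mood worsened. Contrasts between cigarette nicotine levels or e-liquid levels are also diluted by events that carry no information about the products.

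**Working it through.** The plan states no figure on this point, so there is nothing to reproduce. The check is first textual, then a scale illustration.

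**Step 1. How each trigger in section 21.1 treats a participant's starting state**

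| Trigger | Protection against counting a pre-existing state |
|---|---|
| Health Changes Questionnaire (item 1) | Exemption 1b |
| Respiratory Health Questionnaire (item 2) | Exemption 2b |
| Carbon monoxide | Limit depends on the Baseline value (for example, above 50 ppm if Baseline is below 20 ppm) |
| Blood pressure, heart rate | Fixed limits, but the same limits exclude at entry (section 3.6, criteria 20 to 25), so a breach is new relative to screening |
| CES-D (item 3) | None, apart from the carve-out for those already monitored for depression |

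CES-D is the only trigger of these with neither a baseline reference nor a matching entry limit.

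**Step 2. Whom the carve-out covers**

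Monitoring from entry is started by a Prime MD result indicating Major Depressive Disorder, not by CES-D. A participant can score 16 or more on CES-D at screening without that result and so enter unmonitored. These are the participants at issue.

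**Step 3. How many events each can generate**

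An open event is updated, so the effect is one event while it stays open, not one for each of Visits 4, 8 and 12.

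**Step 4. Scale**

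Input from the documents: 480 randomised (section 30). Assumed, because the documents do not give them:
- *p*, the share entering at 16 or more and unmonitored: 5% to 30%
- *q*, the share of those who score 16 or more again on study: 50% to 80%

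Participants with a form and no worsening required = 480 × *p* × *q*.

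| *p* | *q* = 0.5 | *q* = 0.8 |
|---|---|---|
| 0.05 | 12.0 (2.5%) | 19.2 (4.0%) |
| 0.15 | 36.0 (7.5%) | 57.6 (12.0%) |
| 0.30 | 72.0 (15.0%) | 115.2 (24.0%) |

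For one level of a factor (240 participants), halving the extremes gives 6 to about 58. These figures take all 480 as contributing an on-study CES-D; loss before Visit 4 would lower them. Some of the people counted will in fact have worsened. The point is that the rule does not require it.

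**The case against.** The strongest reply is that item 3 is a deliberately conservative prompt for medical review, not a counting rule. It says that a form is completed and the medical monitor advises. Section 29 specifies no adverse event comparison or table. The exemptions in 1b and 2b concern open-ended self-reports and apply only when the description does not otherwise meet the definition of an adverse event. Worsening is also captured separately, since section 28.4 lists change in CES-D as a safety outcome.

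Much of this stands. It is a good reason to leave the form, the review and the follow-up alone, and the CES-D change outcome does preserve a baseline-referenced mood signal. It does not remove the problem in the adverse event data. Section 21.1 names the CES-D among the ways adverse events are identified, section 28.4 makes adverse events a safety outcome, and no rule separates pre-existing scores from new ones.

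A reader might infer four stronger points that the documents do not support:

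- *The rule biases comparisons between arms.* Randomisation balances screening scores in expectation, so the effect is inflation and dilution in all arms.
- *Pre-existing symptoms swamp new cases.* Neither the entry distribution nor the new-onset rate is given.
- *Everyone entering at 16 or more is affected.* Those already monitored are exempt. Section 20 also does not say that a Prime MD result is the only possible route into monitoring, and the BDI is scheduled at every visit if needed.
- *Counting only scores that exceed the screening value would sharpen the comparison.* With 240 per level, the standard error of a risk difference is √(2 × 0.20 × 0.80 / 240) = 3.7 points at an assumed 20% background and √(2 × 0.05 × 0.95 / 240) = 2.0 points at an assumed 5%. That gain would not follow from such a rule, because one point of noise would qualify. For a stable person with four exchangeable scores and no ties, the chance that at least one of the three later scores exceeds the first is 3/4. Regression to the mean lowers this among people with high screening scores, but does not remove it.

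**Conclusion.** The concern holds for participants not already monitored for depression. As written, item 3 records an adverse event for an unchanged or improved score of 16 or more, out of line with how the same section treats other pre-existing conditions and carbon monoxide. The consequence is inflated and diluted mood event counts in all arms, with no bias between arms and no loss of the CES-D change outcome.

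The range from Step 4, 2.5% to 24% of those randomised, shows scale only, since both of its inputs are assumptions. The conclusion itself rests on the text and does not depend on them. It does assume that a completed Adverse Event Form is counted as an adverse event. Section 21.1 implies this, but the plan gives no explicit counting rule.

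**What to change.** Keep the Adverse Event Form, the medical monitor review and the follow-up for every score of 16 or more exactly as written. Then:

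1. In the safety summary, flag CES-D-triggered events and tabulate them by arm separately for screening CES-D below 16 and 16 or more.
2. Treat only the below-16 stratum as new-onset. Read worsening in the 16-or-more stratum from the CES-D change outcome already listed in section 28.4.
3. Reconcile section 21.1 item 3 with items 1b and 2b, so that the text states how a pre-existing high score is to be described in the adverse event data.

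The screening CES-D is already collected, so no new data are needed. The cost is one extra table split and a short clarifying statement. One limit remains: a small move across the threshold, such as 15 to 16, would still appear as new-onset, so the table should be read alongside the change scores.
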